## 3 Study objective(s)

The primary objective of the study is to evaluate the safety and tolerability of subcutaneous (s.c.) administration of DM-101 in adult subjects with birch pollen allergy. A secondary objective is to determine the proportion of study subjects who reach the pre-defined maximum admissible s.c. DM-101 dose in each dosing group.

An exploratory objective of the study is to evaluate the possible effects of repeated s.c. DM-101 dosing on immunological biomarkers in study subjects with birch pollen allergy.

## 4 Design and type of the study

The study is a randomized, double-blinded, placebo-controlled, dose escalation study to evaluate the safety and tolerability of subcutaneous immunotherapy with DM-101 in adults with birch pollen allergy.

## 5 Sample size considerations

After the protocol amendment, a total of 27 subjects were planned to be randomised into the study. For cohort 1, 6 subjects were randomized in a ratio of 2:1 to receive single doses of DM-101 or placebo. For cohort 2, 5 subjects were randomized before the temporary halt of the study, 4 to receive repeated doses of DM-101 and one to placebo. For cohorts 3 and 4, the following allocation was planned:

**Cohorts 3 and 4:** 8 subjects per cohort randomized in a ratio of 3:1 to receive repeated doses of DM-101 or placebo.

## 6 Statistical hypotheses

There are no formal statistical hypotheses set for the study.

## 7 Analysis sets

A subject classification document including a list of protocol deviations with a clinical classification of the deviations and the definition of the analysis datasets will be prepared and

approved after database lock before opening of the randomization code. For cohorts 1 and 2, subject classification was already done prior to opening of the randomization code of these cohorts for the interim analysis and report (documented in Desentum DM-101-C001 Subject Classification Final 18May2020.doc). The subject classification of cohorts 3 and 4 will be done after the database lock of the full database and prior to opening of the randomization code of these two remaining cohorts.

Three main analysis data sets were planned to be constructed. The intent-to-treat (ITT) data set was to include all subjects having received study medication and providing at least a minimum amount of relevant measurements. The safety data set was to consist of subjects having received at least one dose of study medication. The per protocol (PP) data set was to exclude all subjects from the ITT data set who meet any of the predefined criteria in the subject classification document.

## 8 General statistical considerations

The data will primarily be analysed using summary statistics. Summary statistics will include at least the number of subjects, mean, standard deviation, median, minimum and maximum values for continuous variables, and frequencies and percentages for categorical variables. All data collected will be listed by subject, cohort, and treatment. In case inferential statistical analyses are conducted, a 2-sided p-value of less than 0.05 is considered statistically significant.

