### **1.2.1. Study Rationale**

Given the attractive characteristics of DM-101, Desentum aims to pursue its pharmacological development as a novel form of AIT for subjects with birch pollen-driven allergic disease and will now initiate a FIH evaluation. The proposed evaluation of the safety and tolerability of DM-101 is in accordance with the European Medicines Agency (EMA) guideline on the clinical development of products for specific immunotherapy for the treatment of allergic diseases (CHMP/EWP/18504/06). Successful completion of this study will provide the necessary supporting evidence to proceed to further evaluation of the safety and efficacy of a short course of DM-101 AIT in larger clinical trials.

Classical phase I studies in healthy individuals are not appropriate for AIT products, since they do not provide helpful safety information, as non-allergic individuals do not react like allergic subjects and therefore they do not carry the risk of the targeted population. For this reason, the DM-101 FIH study will be conducted in subjects with a history of moderate to severe allergic rhinoconjunctivitis during the birch pollen season and confirmed sensitization to birch pollen allergen.

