### **Revised dose selection rationale for Cohorts 3 and 4**

Based on the safety findings from the initially conducted cohorts of this FIH trial and Desentum's latest laboratory data on the amount of biologically active Bet v 1 in commercially available birch pollen s.c. AIT products, it is considered important to continue this study with a DM-101 dosing scheme that carries low risk of induction of serious allergic reactions. To this end, the study design has been amended to include only 2 additional cohorts (cohorts 3 and 4) where DM-101 will be administered following a very slowly escalating repeat dose regimen, with doses starting from 30 ng, up to a maximum

of 300 ng. The rapid dose escalation over 2 consecutive days (Visit 2, Day 1 and 2) included in the original study protocol (version 1.1) has been omitted. Instead, a slow dose escalation that will take place over 5 bi-weekly dosing visits is proposed.

Dosing in both cohorts, 3 and 4, will start with administration of a single s.c. injection of placebo or 30 ng of DM-101 on Visit 2, followed by a single s.c. injection of placebo or 50 ng of DM-101 2 weeks later (Visit 3). Subsequently, in cohort 3 dosing will continue with single administration of placebo or 100 ng DM-101 on each of the Visits 4 to 6. In cohort 4, Visits 4 to 6 will include s.c. injections of placebo or increasing doses of DM-101 corresponding respectively to 100, 200 and 300 ng (Table 8). The doses of 200 ng and 300 ng will be administered as 2 and 3 s.c. injections of 100 ng respectively, with at least 30 min intervals between injections.

The starting dose of 30 ng has been selected because it was found to be safe and well-tolerated by the subjects who completed cohort 1 of this study. The subsequent 2nd dose of 50 ng and 3rd dose of 100 ng have been selected as modest steps of dose escalation in order to maximise safety. The 100 ng dose level has already been tested as the starting dose of the 4 subjects who received cohort 2 active treatment in this study; in these subjects, 100 ng DM-101 was not associated with the development of significant TEAEs or systemic allergic reactions. In cohort 3, 100 ng is the maximal planned dose that will be administered on subsequent visits until the end of the treatment phase. If this dosing scheme is well tolerated by the cohort 3 subjects, further dose escalation above 100 ng will be attempted in cohort 4 at Visit 4 (200 ng) and at Visit 5 (300 ng).

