### **Cohorts 3 and 4**

The revised dosing scheme of protocol version 2.0 will be applied in these cohorts (cohorts 3 and 4). There will be 6 subjects in each cohort allocated to receive s.c. injections of DM-101 and 2 subjects allocated to receive corresponding placebo injections. The recruitment procedures and subject selection criteria have not been modified for version 2.0 of the study protocol.

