## 10. STATISTICS AND DATA MANAGEMENT

### 10.1. Estimation of Sample Size

A total of 27 subjects will be randomized into the study; additional subjects may be included to replace discontinued subjects in cohorts 3 and 4. Cohort 1 included 6 subjects, and 5 of the planned 8 subjects were included in cohort 2 before the study was temporarily halted. No new subjects will be included in cohort 2 after re-start of the study (Protocol version 2.0). Cohorts 3 and 4 will include 8 subjects each. The selected sample size is not based on any formal power calculations.

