## 13 Analysis of safety variables

The primary endpoint of the study is the number of all treatment-emergent adverse events (TEAEs) in subjects receiving treatment with DM-101, compared to placebo. TEAEs will be MedDRA coded and tabulated by System Organ Class and Preferred Term. Occurrence of single Preferred Terms will be presented by cohort and treatment. In addition, TEAEs will be reported by causality and severity. Both subject and event counts will be summarized. Adverse events occurring prior to first administration of study drug will be listed.

The number and severity of systemic allergic reactions in subjects receiving treatment with DM-101, compared to placebo, will be presented in a similar manner as the TEAEs.

Systemic allergic reactions (SAR) are described with case narratives and will be graded per WAO classification and summarized by cohort and treatment. In addition, an overall summary of SARs by grade, causality, severity, seriousness, and concomitant/additional treatment given (yes/no) will be created. SARs by onset (dosing day and immediate vs delayed (>30 min from dosing)) will be summarized as well. Local injection site reactions (pain, tenderness, erythema/redness, induration/swelling) will be graded on a five-point (0 to 4) scale. These will be summarized by cohort and treatment and presented separately for each cohort (including by injection). Also, a summary by onset (immediate vs. delayed (>30 min from dosing)) will be given and the size of the measured skin reaction for all cohorts (using the collected precision) will be summarized by subject over time and compared to the dose of each injection.

Other safety variables include results from physical examination, vital signs, clinical laboratory values and spirometry. The results will be presented using descriptive statistics and visualizations by cohort, time point and treatment. For the laboratory assessments, all out-of-range values and their clinical significance (CS) (categories: low[CS], low[NCS], normal, high [NCS], high [CS]) will be summarized with shift tables for change from baseline. If feasible, also these parameters and changes from pre-dose to post-dose can be compared to the cumulative dose. Tryptase values will be listed by subject and time point (measured only for subjects with suspected grade 3 or higher systemic allergic reaction or anaphylactic shock).

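### The final safety tables give reaction rates as counts and percentages with no interval, so zero systemic reactions among at most 6 DM-101 subjects at 200 or 300 ng would appear as 0 (0.0%) although risks of up to 39.3% (one-sided) or 45.9% (two-sided) are not excluded

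*SAP*

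**What the plan says.** The protocol plans 27 subjects (section 10.1: "A total of 27 subjects will be randomized into the study") and states that "The selected sample size is not based on any formal power calculations". There are no formal hypotheses, and safety is to be analysed descriptively (Protocol 10.4, SAP 6).

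Cohorts 3 and 4 are each planned as "8 subjects per cohort randomized in a ratio of 3:1" (SAP 5). The cohort description in Protocol 3.2 confirms the active-arm size: "There will be 6 subjects in each cohort allocated to receive s.c. injections of DM-101".

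For reporting, SAP 8 lists "frequencies and percentages for categorical variables" as part of a minimum set of statistics. It adds a two-sided 0.05 convention that applies only if inferential analyses are done. On the reactions of most interest, SAP 13 says: "The number and severity of systemic allergic reactions in subjects receiving treatment with DM-101, compared to placebo, will be presented in a similar manner". In practice this means subject and event counts by cohort and treatment, like those planned for TEAEs in general. It also plans narratives, WAO grades, causality, severity and onset. The table plan in SAP 21.1 follows this pattern and contains no interval.

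The protocol says what the results are for. Section 1.2.1 states: "Successful completion of this study will provide the necessary supporting evidence to proceed to further evaluation of the safety and efficacy" in larger trials. Section 1.2.3 says: "If this dosing scheme is well tolerated by the cohort 3 subjects, further dose escalation above 100 ng will be attempted in cohort 4".

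**The concern.** With six treated subjects, a zero count is a realistic result for systemic reactions even when the true risk is substantial. A percentage alone cannot separate a low risk from a small sample, because 0 of 6 and 0 of 600 both print as 0.0%.

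The documents already reason from small zero counts without stating their precision. Protocol 1.2.3 and 1.4 describe 30 ng as safe on the basis of cohort 1, where 4 subjects received DM-101 (Table 6). They support 100 ng partly because no systemic reaction followed it in the 4 DM-101 subjects of cohort 2. The final tables could invite the same reading for 200 and 300 ng.

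This matters because the product already has a systemic signal. Protocol 4.1 reports systemic allergic reactions in 3 of the 5 cohort 2 participants, under a rapid regimen that went to much higher doses. The study is also meant to support later trials, whose planners will want to know what risk the data rule out.

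**Working it through.** **Sample size.** The plan's only figure is a sum: 6 + 5 + 8 + 8 = 27, which reproduces. At 3:1, 8 × 3/4 = 6 DM-101 subjects in each of cohorts 3 and 4. There is no power or precision statement to reproduce.

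**Denominators by daily dose** (Protocol Table 8, assuming full enrolment, no dropout and no dose adjustment):
- 200 ng and 300 ng: cohort 4 only, so at most 6 DM-101 subjects, one visit each.
- 100 ng in the slow regimen: cohorts 3 and 4, 6 + 6 = 12.
- 100 ng including cohort 2: 12 + 4 = 16. The 4 extra subjects had 100 ng as the first injection of a rapid escalation.

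**Upper bound for zero events.** The exact (Clopper-Pearson) bound for 0 of n is 1 − 0.05^(1/n) one-sided 95%, and 1 − 0.025^(1/n) for the upper limit of a two-sided 95% interval.

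| Result | One-sided 95% | Two-sided 95% upper limit |
|---|---|---|
| 0 of 6 | 1 − 0.05^(1/6) = 39.3% | 1 − 0.025^(1/6) = 45.9% |
| 0 of 12 | 1 − 0.05^(1/12) = 22.1% | 1 − 0.025^(1/12) = 26.5% |
| 0 of 16 | 1 − 0.05^(1/16) = 17.1% | 1 − 0.025^(1/16) = 20.6% |
| 0 of 4 (existing basis at 30 or 100 ng) | 1 − 0.05^(1/4) = 52.7% | 1 − 0.025^(1/4) = 60.2% |

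One or two events are no more precise. From beta quantiles, the two-sided 95% interval is 0.4% to 64.1% for 1 of 6 and 4.3% to 77.7% for 2 of 6.

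**How easily a zero arises.** The chance of no event in n subjects at per-subject risk p is (1 − p)^n. The values of p are illustrative, since the documents give no expected rate.
- n = 6: 0.9^6 = 53.1% at 10% risk, 0.8^6 = 26.2% at 20%, 0.7^6 = 11.8% at 30%.
- n = 12: 0.9^12 = 28.2% at 10%, 0.8^12 = 6.9% at 20%.

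A zero at 200 or 300 ng is therefore more likely than not when one subject in ten would react.

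**Which endpoint.** The point concerns systemic reactions and higher-grade local reactions. It has little force for any related TEAE, because all 4 DM-101 subjects in cohort 1 had one at 30 ng (Table 6).

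**The case against.** The case for leaving the plan alone has several parts.

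- The study is openly descriptive and the SAP 8 list is a minimum, so intervals are allowed. SAP 11 will report how many subjects received each planned dose, and the interim tables print N beside n (%). A statistician can derive the interval from those. This stands and limits the severity. But permission is not commitment, and most readers will not do the calculation. Narratives and grades describe reactions that occurred. They say nothing about what a zero excludes.
- A reader might infer that the step above 100 ng rests on 6 subjects, and so carries the 39% figure. The documents do not support that. Protocol 3.3 bases the step on cohort 3 through Visit 5 together with cohort 4 through Visit 4, which is 12 planned DM-101 subjects at 100 ng, and section 3.2 adds all safety data so far. SAP 8 governs the final analysis. The Safety Review Committee works under section 9 and separate instructions that are not available here.
- A reader might want the committee to receive the same bound. Its review is blinded by default (Protocol 3.3), and a bound on the DM-101 proportion would need treatment codes.
- A reader might take the 0.05 convention as a planned comparison with placebo and criticise its power. No such safety test is planned. The sentence is conditional, and the only exploratory analyses announced concern biomarkers.
- A reader might infer that the plan treats a lack of events as proof of safety. No passage says so, and sections 9.1 and 9.3 set event-based criteria. That a zero will be over-read is a judgement, although sections 1.2.3 and 1.4 make it a reasonable one.

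**Conclusion.** The point holds as a cheap improvement to the final analysis, not as a flaw in the design or the escalation decision. The final tables have no planned measure of precision for reaction rates. At 200 and 300 ng, zero systemic reactions would leave per-subject risks of up to 39.3% (one-sided 95%) or 45.9% (two-sided 95%) unexcluded. At 100 ng the figures for zero events are 22.1% and 26.5% on the planned 12.

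These figures assume that all planned DM-101 subjects receive each dose as scheduled. Fewer would widen the bounds. Section 9.3 halts escalation after a Grade 3 reaction, so results at the higher doses describe only subjects who got that far. At 100 ng, cohort 3 has three planned dosings and cohort 4 has one, so the per-subject risk mixes exposures. The 0 of 16 figure (17.1% or 20.6%) also assumes that a first injection in a rapid escalation is comparable with a slow-regimen dose. It should be no more than a labelled sensitivity figure.

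**What to change.** Add to SAP 13, with a matching entry in the table plan in 21.1:

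*For DM-101 subjects, the proportion with (i) any systemic allergic reaction, (ii) a Grade 2 or higher systemic allergic reaction and (iii) a Grade 3 or higher injection site reaction will be given with an exact Clopper-Pearson two-sided 95% confidence interval, by cohort and by dose level. The denominator at each dose level is all DM-101 subjects in cohorts 3 and 4 who received that dose. A result at 100 ng that adds cohort 2 will be shown only as a labelled sensitivity figure. Zero events will not be described as evidence of safety without the upper limit.*

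Two-sided intervals match the convention in SAP 8. The denominator should be subjects who received the dose, not subjects grouped by the highest dose reached. Grouping by highest dose would put every cohort 4 completer at 300 ng, could leave the 200 ng group empty, and would select on tolerance. The SAP should also say how a reaction is assigned to a dose level, for example to the last dosing visit before onset.

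The cost is one table column and a safety statement that looks less favourable. No new data are needed, and sample size, dosing, stopping criteria and the blinded committee review are unchanged.

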## 9 Demographic and other baseline characteristics

The demographic variables (age, gender, race, ethnicity, height, weight and body mass index) and baseline characteristics (including results of skin prick testing and Bet1v IgE as well as other than Birch common allergen IgE screening levels and pregnancy test results of females of child-bearing potential) and medical history of the subjects will be presented using descriptive summary statistics or frequency tables by cohort and treatment.

## 10 Prior and concomitant medication/treatment

Prior and concomitant medications will be classified according to ATC and reported by ATC1, ATC4, cohort and treatment group using descriptive tables and listings. Any medication started and ended prior to start of study treatment is considered prior medication and medication ongoing or ended after start of study treatment is considered as concomitant medication. Separate summaries for medication used to treat an adverse event will be given.

## 11 Extent of exposure and compliance

Used doses with a cumulative received dose will be summarized descriptively for each cohort and each subject. Also, the numbers of subjects receiving each planned dose and the number of changes from planned doses will be summarized with percentages.

## 12 Analysis of efficacy

Not applicable.

## 13 Analysis of safety variables

The primary endpoint of the study is the number of all treatment-emergent adverse events (TEAEs) in subjects receiving treatment with DM-101, compared to placebo. TEAEs will be MedDRA coded and tabulated by System Organ Class and Preferred Term. Occurrence of single Preferred Terms will be presented by cohort and treatment. In addition, TEAEs will be reported by causality and severity. Both subject and event counts will be summarized. Adverse events occurring prior to first administration of study drug will be listed.

The number and severity of systemic allergic reactions in subjects receiving treatment with DM-101, compared to placebo, will be presented in a similar manner as the TEAEs.

Systemic allergic reactions (SAR) are described with case narratives and will be graded per WAO classification and summarized by cohort and treatment. In addition, an overall summary of SARs by grade, causality, severity, seriousness, and concomitant/additional treatment given (yes/no) will be created. SARs by onset (dosing day and immediate vs delayed (>30 min from dosing)) will be summarized as well. Local injection site reactions (pain, tenderness, erythema/redness, induration/swelling) will be graded on a five-point (0 to 4) scale. These will be summarized by cohort and treatment and presented separately for each cohort (including by injection). Also, a summary by onset (immediate vs. delayed (>30 min from dosing)) will be given and the size of the measured skin reaction for all cohorts (using the collected precision) will be summarized by subject over time and compared to the dose of each injection.

Other safety variables include results from physical examination, vital signs, clinical laboratory values and spirometry. The results will be presented using descriptive statistics and visualizations by cohort, time point and treatment. For the laboratory assessments, all out-of-range values and their clinical significance (CS) (categories: low[CS], low[NCS], normal, high [NCS], high [CS]) will be summarized with shift tables for change from baseline. If feasible, also these parameters and changes from pre-dose to post-dose can be compared to the cumulative dose. Tryptase values will be listed by subject and time point (measured only for subjects with suspected grade 3 or higher systemic allergic reaction or anaphylactic shock).

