**Duration of treatment:**

**Cohort 1:** 1 day, single dose administration.

**Cohorts 2, 3 and 4:** 8 weeks, including 5 bi-weekly administrations

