None of the 4 subjects who receive dosing with DM-101 on Day 1 had Day 2 dosing initiated. In contrast, the 1 subject who received placebo completed Day 1 and 2 dosing with no TEAEs of special interest reported.

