**Table 7. Summary of treatment-emergent adverse events in cohort 2**

Category	DM-101 (N=4) f n (%)	Placebo (N=1) f n (%)	Total (N=5) f n (%)
Any TEAE	56 4 (100.0)	2 1 (100.0)	58 5 (100.0)
IMP-related TEAEs	50 4 (100.0)	0 0 (0.0)	50 4 (80.0)
Severe TEAEs	0 0 (0.0)	0 0 (0.0)	0 0 (0.0)
Serious TEAEs	0 0 (0.0)	0 0 (0.0)	0 0 (0.0)
TEAE leading to discontinuation*	2 2 (50.0)	0 0 (0.0)	2 2 (40.0)

Abbreviations: TEAE = Treatment-emergent adverse event; n = the number of subjects with at least one TEAE; f = the number of TEAEs

\*One of the discontinued subjects had 2 reasons for discontinuation, both withdrawal of consent and 2 Grade 3 local injection site reactions after 2 injections of IMP.

Based on the findings of the interim analysis and in order to ensure the safety of the study subjects, the dose and dose escalation scheme for further cohorts were decided to be revised.

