#### **Follow-up Period:**

All subjects will return to the research site for a Follow-up visit (Visit 3 for cohort 1 and Visit 7 for cohorts 2-4), for medical assessment and collection of blood samples. The Follow-up visit will take place approximately 4 weeks (28 days ± 3 days) after the last dosing of each subject.

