## 8. ADVERSE EVENTS

The Investigator and his staff are responsible for detecting, documenting and reporting events that meet the definition of an AE. Adverse events will be reported, irrespective of whether they are volunteered, elicited, or noted on physical examination or medical review, throughout the study, from the signing of the ICF until the Follow-up visit.

AEs occurring prior to the first treatment administration, but after obtaining informed consent will be reported separately from TEAEs, which will be of particular interest.

Definitions of AEs and serious adverse events (SAE) and the documentation and reporting of them within this study will follow the GCP, EU and Finnish national guidance.

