## **10.9. Analysis of Safety Variables**

The primary endpoint of the study is the number of all TEAEs in subjects receiving treatment with DM-101, compared to placebo. TEAEs will be MedDRA coded and tabulated by System Organ Class and Preferred Term. Occurrence of single Preferred Terms will be presented by cohort and treatment. Also, separate tabulations by treatment will be provided. For each preferred term, the average number of events will be calculated. In addition, TEAEs will be reported by causality and severity.

The number and severity of systemic allergic reactions in subjects receiving treatment with DM-101, compared to placebo, will be presented in a similar manner as the TEAEs.

Local injection site reactions (pain, tenderness, erythema/redness, induration/swelling) will be graded on a five-point (0 to 4) scale. These will be presented and summarized by cohort and treatment.

Other safety variables include results from physical examination, vital signs, clinical laboratory values and spirometry. The results will be presented using descriptive statistics by cohort and treatment.

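### The primary TEAE count has no exposure denominator, so reaction-driven stopping on DM-101 would understate the contrast with placebo

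*SAP*

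**What the plan says.** SAP Section 13 defines the endpoint: "The primary endpoint of the study is the number of all treatment-emergent adverse events (TEAEs) in subjects receiving treatment with DM-101, compared to placebo". On how it is summarised, it says "Both subject and event counts will be summarized". Protocol Section 10.9 adds "For each preferred term, the average number of events will be calculated", without naming a denominator, and the SAP text does not repeat this. Neither document plans a TEAE rate per injection, per dosing visit or per unit of time observed.

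Protocol Section 8 collects AEs "throughout the study, from the signing of the ICF until the Follow-up visit". Section 3.2 ties that visit to the individual: "The Follow-up visit will take place approximately 4 weeks (28 days ± 3 days) after the last dosing of each subject". Section 6.4 says the same for cohorts 3 and 4. The synopsis gives the planned course in cohorts 2 to 4 as "8 weeks, including 5 bi-weekly administrations".

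Section 9.2 discontinues a subject's dosing after defined systemic or injection site reactions. The replacement provision in Section 4.1 covers only subjects who leave for reasons other than a TEAE.

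**The concern.** The length of the AE window and the number of injections both depend on when a subject stops, and some of the stopping rules are triggered by the events being counted. Reaction-driven stopping is more likely on active allergen than on diluent. The arm with more intolerance may therefore have fewer injections and fewer days in which to record further events. The comparison with placebo would then be smaller than under full dosing and an equal window.

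At stake is how the trial's main safety contrast is read. No test or error rate is involved, because the documents state no formal hypothesis (Protocol Section 10.4, SAP Section 6).

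**Working it through.** **1. Observation and injections by last dosing visit, cohorts 3 and 4.** Dosing days come from Protocol Table 11 and injections from Table 8. Follow-up day = day of last dosing + 28. A full course ends at 56 + 28 = Day 84, which reproduces Table 11.

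| Last dosing | Day | Follow-up day | Share of 84 days | Injections, cohort 3 | Injections, cohort 4 |
|---|---|---|---|---|---|
| Visit 2 | 0 | 28 | 33% | 1 of 5 | 1 of 8 |
| Visit 3 | 14 | 42 | 50% | 2 of 5 | 2 of 8 |
| Visit 4 | 28 | 56 | 67% | 3 of 5 | 3 of 8 |
| Visit 5 | 42 | 70 | 83% | 4 of 5 | 5 of 8 |
| Visit 6 | 56 | 84 | 100% | 5 of 5 | 8 of 8 |

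**2. Cohort 2, from the protocol's own data.** Table 7 gives 56 TEAEs in 4 DM-101 subjects and 2 in 1 placebo subject (56 + 2 = 58, as stated). Section 1.2.3 says "None of the 4 subjects who receive dosing with DM-101 on Day 1 had Day 2 dosing initiated", so each had at most 6 injections, 4 × 6 = 24 in all. The placebo subject completed both days, 6 + 3 = 9 injections.

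- Per subject: 56/4 = 14 v 2/1 = 2, ratio 7.0.
- Per injection: at least 56/24 = 2.33 v 2/9 = 0.22, ratio at least 10.5. The 24 is a ceiling, so 10.5 is a floor.
- Per subject-day, assuming Follow-up took place 28 days after the last dose (Day 1 v Day 2, so about 28 v 29 days): (56/112)/(2/29) = 7.25.

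The injection denominator changes the contrast by a factor of at least 10.5/7.0 = 1.5. The time denominator hardly changes it.

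**3. Illustration for cohort 3, with assumed rates.** The rates are borrowed from Table 6 (cohort 1, one 30 ng dose, 28-day follow-up). DM-101 had 5 related TEAEs in 4 subjects, 1.25 per dosing. Placebo had 3 TEAEs in 2 subjects, 1.5 per 28 days, taken as background in both arms.

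- Full course, DM-101: 5 × 1.25 + 3 × 1.5 = 10.75.
- Full course, placebo: 3 × 1.5 = 4.5. Ratio 10.75/4.5 = 2.39.
- DM-101 subject stopping after Visit 3: 2 × 1.25 + (42/28) × 1.5 = 4.75, a shortfall of 10.75 − 4.75 = 6.0 events.
- With 2 of 6 stopping after Visit 3, the total is 2 × 4.75 + 4 × 10.75 = 52.5 events.
  - Count ratio: (52.5/6)/4.5 = 1.94.
  - Per subject-day: 52.5/(2 × 42 + 4 × 84) = 0.125 v 4.5/84 = 0.0536, ratio 2.33.
  - Per dosing visit: 52.5/(2 × 2 + 4 × 5) = 2.19 v 4.5/5 = 0.90, ratio 2.43.

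| DM-101 subjects (of 6) stopping after Visit 3 | Count ratio | Ratio per subject-time | Ratio per dosing visit |
|---|---|---|---|
| 0 | 2.39 | 2.39 | 2.39 |
| 1 | 2.17 | 2.36 | 2.41 |
| 2 | 1.94 | 2.33 | 2.43 |
| 3 | 1.72 | 2.30 | 2.46 |
| 6 | 1.06 | 2.11 | 2.64 |

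The two rates lie on either side of the full-course value, and both stay closer to it than the count does. The model adds no extra events for the reactions that trigger stopping. Such events would raise the count with or without stopping, so they leave the 6.0 shortfall unchanged.

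**The case against.** The case against making much of this is substantial.

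- The analysis is descriptive, all data are listed by subject, and no decision rule uses the TEAE ratio. Stopping and escalation rest on graded reactions and Safety Review Committee review. This stands and limits the consequence.
- Intolerance is not hidden. The SAP already plans doses received and cumulative dose (Section 11), the proportion reaching the pre-defined cumulative dose (Section 14), discontinuations with reasons (Section 16), AEs leading to discontinuation (Table 14.3.2.6), injection site reactions by injection, and systemic reactions by dosing day (Section 13). This stands, and it removes the need for a new rate for injection site reactions. But none of these outputs puts a denominator under the primary count.
- Early stopping in cohorts 3 and 4 may be uncommon. Under Protocol Section 9.3 one Grade 3 reaction adjusts the dose, and the visits continue. Visit 2 is a single injection, so the graded-reaction rules would stop a subject there essentially only for a Grade 4 reaction. A Grade 4 systemic reaction suspends dosing in the study as a whole. This stands: the first row of the table above is the least likely.
- Rates have faults of their own. Per-time rates in early stoppers can be inflated because an event caused the stop, and injections differ in dose. This also stands, and it is why rates should not take over as the primary summary.

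Two stronger readings are tempting. A reader might infer that intolerance makes DM-101 look safer than placebo, even with no drug effect. That contradicts itself, because without a drug effect reaction-driven stopping would not concentrate on DM-101. A reader might also take cohort 2 as proof that shortened follow-up distorts the count. It is not: the windows there were about 28 v 29 days, and the raw 56 v 2 already showed the signal.

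**Conclusion.** The point holds as a conditional understatement. The primary contrast is a count with no exposure denominator, the AE window closes 28 days after each subject's own last dose, and reactions can stop dosing. Sections 8.5 and 8.7 of the protocol follow existing events to their outcome, but no text keeps collection of new events open to Day 84 for a subject who stops early.

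If stopping falls mainly on DM-101, the count contrast is smaller than under full exposure. The documents do not support saying that the DM-101 count would fall below placebo.

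The documents' own data give one size: in cohort 2, 7-fold per subject v at least 10.5-fold per injection, with doses per injection ranging from 100 to 5,000 ng. For cohorts 3 and 4 the size depends on the number of early stoppers, which is not given. The fall from 2.39 to 1.94 with 2 of 6 stopping after Visit 3 is an illustration. It rests on rates from 6 cohort 1 subjects and on constant rates per dosing and per day. If nobody stops early, the exposure-adjusted ratios equal the count ratio.

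**What to change.** In SAP Section 13 and Protocol Section 10.9, keep the TEAE counts as the primary summary. Beside them, by cohort and treatment, add for TEAEs and for systemic allergic reactions:

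- events per injection given (or per dosing visit);
- events per subject-week, from first dose to Follow-up or last contact.

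Show the denominators in Table 14.3.2.1 and in the summary of systemic allergic reactions. The latter is the safety Table 14.3.3.1; SAP Section 21.1 also gives that number to the IgE table, so name the table by its title. State that the DM-101 v placebo contrast is read with counts and rates together.

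Do not switch the primary statement to rates whenever a subject stops early. That would make the main summary depend on the data, and the two rates can disagree.

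The cost is two extra columns in planned tables. Dose dates and times are recorded (Protocol Section 5.5) and exposure is already tabulated (Table 14.3.1.1), so no new data are needed. The downside is instability with 2 placebo subjects per cohort, unequal doses per injection and possible inflation of per-time rates in early stoppers. Label the rates as supplementary.
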